### 3 OBJECTIVES AND ENDPOINTS

OBJECTIVES	ENDPOINTS	JUSTIFICATION FOR ENDPOINTS
Primary: To assess the improvement in tissue visualization in CBCT images	Improvement in image quality and quantitative accuracy as measured by established objective image quality metrics.	We will evaluate absolute CT number error, image artifact amplitude, and contrast to noise ratio, which are metrics that quantify the image quality. We hypothesize that values of these metrics will be improved in CBCT images acquired with the 2D grid.
Secondary: To evaluate the accuracy of tissue delineation in CBCT images by auto-segmentation software.	Similarity of anatomical structures delineated by auto-segmentation software and expert observers, as measured by established similarity metrics.	Auto-segmentation software is a highly desired tool that is expected to generate delineations similar to delineations by human observers. We will use delineations by observers as the gold standard. We will measure the similarity between the auto-segmented delineations and observer delineations.
Tertiary/exploratory: To assess the utility of CBCT images in qualitative and quantitative imaging tasks	Improvement in qualitative and quantitative imaging tasks as measured by quality metrics pertinent to each task	CBCT images are used in a wide variety of tasks. Some task examples are tissue delineation for treatment adaptations, radiomics feature evaluation, radiotherapy dose calculations, and target localization. Thus, image quality metrics will be identified for each task, and the utility of CBCT images in each task will be evaluated using the quality metrics associated with each task.

### 4 STUDY DESIGN

#### 4.1 OVERALL DESIGN

This is a Pilot study that investigates the CBCT image quality improvement provided by the 2D antiscatter grid technology. The primary objective is to assess the improvement in tissue visualization and CT number accuracy, as measured by objective image quality metrics.

- This is a single arm study, where all participants will be scanned with a CBCT system equipped with 2D antiscatter grid technology, referred to as research CBCT with 2D grid. Each participant will also be scanned with a standard clinical CBCT, which will serve as the baseline, or control. Thus, the image quality improvement in research CBCT with 2D grid will be assessed with respect to standard clinical CBCT without 2D grid.
- We anticipate enrolling a total of 42 participants. Groups (1) and (3) will have, in any combination, the collective total value of 21 participants. Group (2) will have 11

participants and Group (4) will have 10 participants. The groups are described as the following:

**Group (1), Photon therapy patients with treatment sites in abdomen or pelvis:** It is particularly challenging to use CBCT to visualize organ boundaries in the abdomen. Disease sites in the abdomen, e.g. the pancreas and liver, are particularly likely to benefit from “online” adaptive radiation therapy due to the proximity of the gastrointestinal tract to targets (online: plan is modified while the patient is on the treatment couch using volumetric setup images).

**Group (2), Photon therapy patients with treatment sites in prostate or prostate bed:** Due to the large tissue volume in the pelvis, scatter is more pronounced, and tissue visualization is degraded. Since larger patients generate more scatter, the image quality is also patient-size dependent. Hence, we will have two subgroups; subgroup stratification will be based on the patient left-right separation at pelvis level (subgroup 1:  $< 40$  cm, subgroup 2:  $\geq 40$  cm). 5 patients will be enrolled in subgroup 1 and 6 patients will be enrolled in subgroup 2. These “small” and “large” pelvis subgroups will allow evaluation of the effect of patient size on the consistency of organ delineation. The threshold of 40 cm comes from our clinical observations; CBCT images from patients with 40 cm (or more) separation are of noticeably lower quality.

**Group (3), Photon therapy patients with treatment sites in head and neck:** The head and neck is another region where large changes in normal tissues and tumors occur throughout the course of treatment. Thus, it will benefit from CBCT-based treatment monitoring and adaptations.

**Group (4), Patients who are treated for cancers in prostate or prostate bed with Proton Therapy:** Selection criteria will be same as the prostate cancer patients in Group (2); however, CBCTs will be acquired with a CBCT system designed for Proton Therapy.

The same imaging workflow will be used for all patient Groups (1)-(3), and each participant will receive one research scan. Group (4) participants will be enrolled in the University of Florida Health Proton Therapy Institute, and they will receive two research CBCT scans.

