Analysis of radiomics feature extraction accuracy: In each image set, we will extract series of radiomics features, such as HU value statistics (e.g. mean, variance, and kurtosis), and texture features, such as gray-level co-occurrence matrix, wavelets, local entropy. Accuracy and repeatability of radiomics features in CBCT (both standard and 2D grid CBCT) and gold standard helical CT will be evaluated using Lin's concordance correlation coefficient (CCC) as in Zhao's work [35]. Statistical analysis details of other potential exploratory studies, such as qualitative and quantitative image quality evaluations, and CBCT-based dose calculations will be determined on an ad hoc basis.

The analysis of TrueBeam (Groups 1-3) and Proteus (Group 4) CBCT images. An image quality difference is expected between TrueBeam and Proteus CBCT due to differences in system design (e.g. TrueBeam has bow tie filter, whereas Proteus does not have one), and image reconstruction chain. Therefore, in the primary analysis, we will analyze the data from patient Groups 1-3 (TrueBeam) and Group 4 (Proteus) separately. This way, we will eliminate potential, system-specific image quality bias. In a subgroup analysis, we will investigate the differences in the study results of Groups 2 and 4 (i.e. prostate cancer patients scanned with TrueBeam and Proteus, respectively).

---

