##### 9.4.6.1 SUB-GROUP ANALYSES

1) Subgroup analyses of image quality metrics will be performed for three anatomical site groups:

- Head and Neck
- Pelvis and abdomen
- Prostate or prostate bed

2) A sub-group analysis of image quality metrics will be performed based on the patient size, as measured by the participant's lateral separation in the imaged volume:

- Lateral separation less than 30 cm
- Lateral separation between 30 and 40 cm
- Lateral separation more than 40 cm

3) Participants in the prostate group will be scanned using two substantially different CBCT systems. To investigate the effect of CBCT system on image quality, the following subgroups will be analyzed separately.

- Prostate and prostate bed subgroup scanned with photon therapy CBCT.
- Prostate and prostate bed subgroup scanned with proton therapy CBCT.

For each subgroup, image quality metrics extracted from CBCT scans with 2D grid and standard clinical CBCT scans will be compared in a pairwise fashion. 95% Confidence Intervals for the image quality metrics (primary objective) will be calculated and reported for each of the subgroups. And the pairwise comparisons between subgroups will be conducted by comparing the 95% Confidence Intervals.

---

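### The Group 2 versus Group 4 comparison of CBCT systems is open to confounding by patient size, because only Group 2 has a stated size split and the comparison is not adjusted for size

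*Combined protocol and SAP*

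**What the plan says.** Section 4.1 stratifies Group 2 by left-right separation at pelvis level: "5 patients will be enrolled in subgroup 1 and 6 patients will be enrolled in subgroup 2", with subgroup 1 below 40 cm and subgroup 2 at 40 cm or more. The reason given is that "Since larger patients generate more scatter, the image quality is also patient-size dependent", and that "CBCT images from patients with 40 cm (or more) separation are of noticeably lower quality".

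For Group 4, section 4.1 states the number ("participants and Group (4) will have 10 participants") and adds "Selection criteria will be same as the prostate cancer patients in Group (2". It gives no small/large split for these 10 patients, and neither does any other section.

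The comparison of the two groups is planned in two places. Section 9.4.1 says that "we will investigate the differences in the study results of Groups 2 and 4". Section 9.4.6.1 item 3 gives the purpose: "To investigate the effect of CBCT system on image quality, the following subgroups will be analyzed separately". The same section compares subgroups by setting their 95% confidence intervals side by side. The mixed model in 9.4.2 has a random patient effect and names no size covariate. Size is a separate subgroup analysis (9.4.2; 9.4.6.1 item 2) and is not crossed with CBCT system. Section 9.4.5 describes participants by lateral separation group and by system type.

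**The concern.** According to the study population text in section 2.1, Group 4 exists because the grid may perform differently on the two kinds of gantry. Groups 2 and 4 share a disease site, so their contrast is the natural place to look for such a difference.

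Group 2 is enriched to 6/11 large patients by design. If Group 4 simply takes the proton patients who present, its share of large patients may be quite different. The protocol itself names size as a driver of image quality, so a difference between the groups could come from the system, from size, or from both. The planned analysis cannot separate them, and random imbalance will not reliably average out with 11 against 10 patients. What is at stake is the estimated difference in grid benefit between the two systems.

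**Working it through.** **Counts.** The stated numbers agree: 5 + 6 = 11 in Group 2, and 21 + 11 + 10 = 42 overall. The large share in Group 2 is 6/11 = 54.5%. The plan gives no power, effect size or standard deviation for Group 2 versus Group 4, so there is no such figure to reproduce.

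**If the split was meant to carry over.** The nearest divisions of 10 are 5/5 (50% large) and 4 small/6 large (60% large). The imbalance against Group 2 would be 54.5 − 50 = 4.5 or 60 − 54.5 = 5.5 percentage points, which is negligible.

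**If it was not.** Let q be the large share in Group 4 and D the difference in grid effect (log scale) between large and small patients. With S2 and S4 the grid effects in small patients on each system, and D the same on both:

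- Group 2 mean effect = S2 + (6/11) × D
- Group 4 mean effect = S4 + q × D
- Difference = (S2 − S4) + (6/11 − q) × D

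The last term is the bias. As a ratio it is exp[(6/11 − q) × ln(benefit in large / benefit in small)]. For q = 10% and benefits of 2.0 and 1.4: exp(0.4455 × 0.3567) = 1.172.

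The documents give neither q nor D. The values below are assumptions chosen to show a range. The binomial columns treat Group 4 as 10 independent patients. The last three columns set D to one within-stratum standard deviation (SD) of the paired log difference. The last two come from 20,000 simulated trials of 11 versus 10 with no true system effect.

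| Assumed q | Imbalance (points) | P(5 or 6 large of 10) | P(none large) | Bias ratio, 2.0 v 1.4 | Bias ratio, 1.6 v 1.4 | Bias, D = 1 SD | 5% t-test rejects | 95% CIs do not overlap |
|---|---|---|---|---|---|---|---|---|
| 10% | 44.5 | 0.2% | 35% | 1.172 | 1.061 | 0.45 SD | 13% | 2.3% |
| 20% | 34.5 | 3.2% | 11% | 1.131 | 1.047 | 0.35 SD | 9% | 1.3% |
| 30% | 24.5 | 14% | 3% | 1.091 | 1.033 | 0.25 SD | 6% | 0.7% |
| 40% | 14.5 | 31% | 0.6% | 1.053 | 1.020 | 0.15 SD | 5% | 0.6% |
| 54.5% | 0 | 47% | <0.1% | 1.000 | 1.000 | 0 | 4% | 0.3% |

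Above 54.5% the sign reverses: at q = 70% the imbalance is −15.5 points.

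**Which quantity is compared.** The formula assumes that paired with-grid minus without-grid differences are compared. Section 9.4.2 calculates intervals for each metric and each CBCT type, and 9.4.6.1 compares subgroups by intervals for the metrics. If those are intervals for the metric values themselves, D becomes the whole effect of size on the metric, not only its effect on the grid benefit. The plan does not say which is meant.

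**The case against.** The sentence on Group 4 can fairly be read as carrying the size strata over. Eligibility in section 5 is common to the study, so beyond site and modality the 40 cm stratification is the only enrolment rule particular to Group 2. A reader might infer that section 4.1 contradicts itself because 5 + 6 does not make 10. The documents do not support that: 5/5 or 4/6 is the same rule applied to 10 patients. What is missing is a number and a clear statement. This part of the objection stands.

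Each patient is their own control on the same system (section 4.2), so the main effect of size cancels from a paired difference. That stands if paired differences are what is compared, which the plan leaves unstated. Size as a modifier of the grid benefit would remain. The size subgroups in 9.4.2 and 9.4.6.1 examine it, but not within the system comparison. The tables in 9.4.5 could reveal an imbalance and would not correct it.

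The magnitudes rest on assumptions. Section 2.2 offers only a twofold gain in contrast-to-noise ratio in pelvis-sized phantoms, with nothing by patient size. This stands, and the top of the range needs both extreme assumptions.

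System is also tied to site, to the bow-tie filter and reconstruction chain (9.4.1), and to the baseline: section 6.1.1 describes removing a standard radiographic grid only on the TrueBeam. Adjusting for size leaves all of these in place. That is true, but they belong to the system contrast or cannot be separated from it. Patient size can be measured and adjusted for.

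**Conclusion.** The comparison is open to confounding by size; it is not shown to be confounded. The Group 4 size mix is unknown, and the bias is zero if about 55% of its patients are large. Under the assumed inputs the spurious difference in grid benefit runs from 2% to 17%, or from 0.15 to 0.45 SD when size modifies the benefit by one SD.

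The harm is a possibly biased estimate in a subgroup comparison of 11 versus 10 patients in a pilot study. A reader might infer that the trial is likely to declare a false system difference. The check does not support that: with D at one SD, non-overlapping intervals arise in only 0.3% to 2.3% of runs. Nor is the primary analysis affected, since section 9.4.1 analyses Groups 1–3 and Group 4 separately and each patient is compared with themselves. The point still merits correction, because the protocol names size as a determinant of image quality and then leaves it out of the one planned comparison of systems within a common disease site.

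**What to change.** In 9.4.1 and 9.4.6.1 item 3:

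- State that Groups 2 and 4 are compared on the paired log difference, with grid minus without grid.
- Estimate the system difference from a model with CBCT type × system, adjusted for lateral separation and CBCT type × lateral separation.
- Report the unadjusted comparison as supportive.
- Tabulate lateral separation by system.
- State that the adjusted result relies on extrapolation if Group 4 has few or no patients at 40 cm or more.

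In 4.1, state whether the 40 cm split applies to Group 4.

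No enrolment quota is required. A target of five large Group 4 patients could be costly: at a large share of 10% or 20% it would take about 5/0.10 = 50 or 5/0.20 = 25 eligible proton patients on average.

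The cost is wording, plus one or two degrees of freedom among 21 patients. Lateral separation is already needed for 9.4.5 and 9.4.6.1, so no new data or patients are involved. The site, system and baseline-grid differences remain part of the contrast, and the report should say so.

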## 4.2 SCIENTIFIC RATIONALE FOR STUDY DESIGN

**Evaluation of CBCT image quality from a clinical perspective:** An essential clinical task in CBCT-guided radiation therapy is visualization of organ and tumor boundaries; clinicians often overlay MDCT images (acquired at treatment planning phase) and CBCT images (acquired at treatment delivery phase) to assess differences in tissue shapes and positions during the course of radiation therapy. Since these two image sets are acquired days or even weeks apart, geometric changes in tissue/organ boundaries between two image sets may imply under-dosing of tumors and/or over-dosing of normal tissues. In *better-quality* CBCT images, clinicians can visualize tissue boundaries more accurately and consistently.

Therefore, quality of research CBCT scans with 2D grid will be evaluated with respect to standard clinical CBCT scans without 2D grid (i.e., the control scan). Objective image quality metrics, such as absolute CT number error, artifact amplitude and contrast to noise ratio, will be extracted from each CBCT scan and the change in image quality metrics will be evaluated with

respect to the control scans. Similar studies have been performed to assess the quality of CBCT images in the context of image-guided radiation therapy [30, 31]. In addition, an observer study will be conducted, and consistency of tissue delineations by observers will be evaluated to assess the effect of CBCT image quality on tissue structure boundary visualization [32, 33].

Standard and research CBCT scans with 2D grid will be acquired on the same study participant, by using identical scan parameters. This approach addresses the following challenges associated with image quality comparisons.

- CBCT image quality depends on patient-specific factors such as patient size and shape, anatomical site of imaging study, and patient motion. By using the same patient and anatomical site for both standard and research scans, dependence of image quality on patient-specific variables is minimized.
- CBCT image quality depends on the imaging system characteristics and imaging dose. For each participant, both standard and research CBCT scans will be acquired using the same dose and scan parameters and using the same CBCT system. This approach minimizes dose and system specific effects on image quality.

### 4.3 JUSTIFICATION FOR DOSE

Our study quantifies the image quality improvement in research CBCT scans acquired with the 2D grid, with respect to standard clinical CBCT scans that serve as the control. All imaging parameters are kept the same for both scans. Therefore, imaging dose in research CBCT scan with 2D grid will be the same as the standard clinical CBCT scan.

### 4.4 END OF STUDY DEFINITION

The study will be complete after the last study participant's CBCT scans are acquired. There will not be any follow-up visits.

## 5 STUDY POPULATION

### 5.1 INCLUSION CRITERIA

In order to be eligible to participate in this study, an individual must meet all of the following criteria:

1. Provision to sign and date the consent form.
2. Stated willingness to comply with all study procedures and be available for the duration of the study.
3. Be a male or female aged 18–100.

4. Participants who will be treated or are currently being treated with CBCT-guided photon therapy for prostate or prostate-bed, abdomen head and neck, or pelvic cancers, or with image-guided proton therapy for prostate or prostate bed cancer.

## 5.2 EXCLUSION CRITERIA

An individual who meets any of the following criteria will be excluded from participation in this study:

1. Metallic implants in the CBCT scan volume, such as hip prostheses or spine stabilization hardware. Patients with pacemakers, defibrillators, or other implanted electronic devices. Dental implants, fillings, or fiducial markers may be acceptable, and the decision for inclusion/exclusion will be on a case-by-case basis, by reviewing prior CT images of the study candidate. Patient's prior CT images will be reviewed by the PI or the site PI.
2. Patients who do not have the ability to lie still for the duration of his/her CBCT imaging and treatment should be excluded. If image artifacts in prior scans are deemed excessive, the patient will be excluded from the study.
3. Known pregnancy. (Per SOC, a pregnancy test will be performed prior to CBCT scan on Day 1. At this time, women of child-bearing potential (WOCBP) will receive a pregnancy test to re-confirm eligibility).
  - Women of child-bearing potential are described as:
    - Age 55 or younger who have not had a negative pregnancy test within 3 days. This excludes patients who have had tubal ligation or are already post-menopausal.

## 5.3 LIFESTYLE CONSIDERATIONS

There are no restrictions regarding lifestyle considerations.

## 5.4 SCREEN FAILURES

Participant may be re-screened for eligibility with documented approval from the Sponsor-Investigator or site PI.

## 5.5 STRATEGIES FOR RECRUITMENT AND RETENTION

The target sample size is 42 participants. Study participants will be recruited from patients treated in the following institutions:

- Department of Radiation Oncology, University of Colorado Hospital.

- University of Florida Health Proton Therapy Institute (UFHPTI).

Both males and females that meet the eligibility criteria can participate in our study. Based on patients treated in our department last year, we expect 50% of patients offered participation to be male, and 50% to be female for the abdomen, pelvis, and head and neck cancer subgroups.

Patients from any racial or ethnic background that meet the eligibility criteria can participate in our study. Based on the patient statistics treated in our department, we expect the following ethnic/racial composition: 20% of participants to be of Hispanic ethnic background, 20% of African American race, 50% of white race, and 10% to be composed of other racial or ethnic groups such as American Indian and/or Asian.

## 6 STUDY INTERVENTION

### 6.1 STUDY INTERVENTION(S) ADMINISTRATION

#### 6.1.1 STUDY INTERVENTION DESCRIPTION

Before each intervention, the 2D grid will be installed into the CBCT system by personnel previously trained in the installation procedure. Following installation, the research CBCT scan will be acquired by radiation therapists by using the same protocol as in a standard clinical scan. It is estimated that the intervention will be completed in less than 30 minutes. Research CBCT scan can be performed either before or after study participant's radiation treatment session. Both standard clinical scan and research CBCT scan will be performed on the same day.

Two different CBCT systems will be used for the study interventions depending on the study site:

- 1) At University of Anschutz Medical Campus: Participants will be treated with CBCT guided photon therapy. Varian TrueBeam system (Varian Medical Systems, Palo Alto, CA) will be used for acquiring both standard clinical and research CBCT scans. TrueBeam CBCT has a standard radiographic antiscatter grid (Model name: Smit Rontgen. Manufactured by Philips, Best, Netherlands). Before acquiring the research CBCT scan (the study intervention), radiographic grid will be removed from the CBCT image receptor, and the 2D grid assembly will be installed. After research CBCT scan, 2D grid will be uninstalled and the radiographic grid will be reinstalled on the image receptor. Subsequently, the imaging system will be calibrated to bring the CBCT system back to its standard clinical configuration.
- 2) At UFHPTI: Participants will be treated with image-guided proton therapy. IBA Proteus system (Ion Beam Applications SA, Louvain-la-Neuve, Belgium) will be used for acquiring both standard and research CBCT scans. Before acquiring the research CBCT scan, the 2D grid assembly will be installed. After research CBCT scan, 2D grid will be

uninstalled, and the CBCT system will be brought back to its standard clinical configuration.

2D grid installation/deinstallation training will be conducted by the PI or other team members trained by the PI. For the Proton Therapy CBCT scans, installation procedures will be developed in collaboration with staff from UFHPTI. The role of each staff and study investigators during 2D grid installation/deinstallation procedure will be identified clearly, and their training will be documented.

[figure not shown]
2D grids prototypes are not participant-specific, but they will be designed specifically for each CBCT system at Anschutz Medical Campus and UFHPTI due to differences in CBCT system geometries. 2D grids will be assembled by PI's team at University Colorado Anschutz Medical Campus. Prototypes will be returned to the PI at the end of the study.

In the photon therapy cohort, the standard clinical CBCT scan, which serves as the control, will be acquired using the standard CBCT system as part of the standard clinical care. In the proton therapy cohort, the standard clinical CBCT scan will be acquired as an additional scan, it will not be part of the standard clinical care. It is important to reiterate that research CBCT scan acquired with the 2D grid will not be used in any way during participant's standard clinical care.

[figure not shown]
Cleaning, sterilization or high-level disinfection is not needed, since 2D grid assembly is not in contact with the patient.

[figure not shown]
